## 9.3.3 IgE and IgG4

Blood samples to measure peanut IgE and peanut-specific IgG4 levels, and total IgE levels will be collected prior to the Screening DBPCFC and prior to the Exit DBPCFC. Peanut-specific IgE/IgG4 ratio will be calculated, listed by subject, and summarized by visit and treatment group. Results outside the limits of quantification will be displayed as less than the lower limit of quantification (LLOQ), or greater than the upper limit of quantification (ULOQ), as appropriate. These values will be summarized as either the LLOQ, or the ULOQ. If the peanut IgE or peanut-specific IgG4 is outside of the limits of quantification, the IgE/IgG4 ratio will be calculated using the LLOQ or ULOQ as appropriate.

Results will be provided by a central laboratory and summarized by visit and treatment group, using the geometric mean and standard deviation in lieu of arithmetic mean and standard deviation. 95% confidence intervals, based on the geometric calculations, will also be provided. Ratios of post-baseline visit to baseline and ratio of those ratios of treatment groups, where applicable, will be presented similarly. All results will be displayed for the ITT population.

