#### 4 SAMPLE SIZE CONSIDERATIONS

Sample size calculations are based on the primary efficacy analysis of the desensitization response rate. A true placebo response rate of 25% or less among subjects who undergo the Exit DBPCFC is assumed. Those individuals who fail to achieve the daily dose target or withdraw prematurely will be treated as non-responders. This study will enroll approximately 50 subjects randomly assigned in a 1:1 ratio of active to placebo.

If 3 subjects in each arm (about 12%) do not undergo the Exit DBPCFC, then the effective placebo response rate in the ITT analysis is assumed to be 22% or less. With a 2-tailed (alpha=0.05) test, there is at least 80% power to detect an effective CPNA response rate of 58.7 % or more, which corresponds to a CPNA response rate of 66.7% or more among those who undergo the Exit DBPCFC.

If 5 subjects in each arm (about 20%) do not undergo the Exit DBPCFC, then the effective placebo response rate in the ITT analysis is assumed to be 20% or less. With a 2-tailed (alpha=0.05) test, there is at least 80% power to detect an effective CPNA response rate of 56.6% or more, which corresponds to a CPNA response rate of 70.75% or more among those who undergo the Exit DBPCFC.

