## 6.5 Significance Level

Unless stated otherwise, all statistical tests will be two-sided, with a significance level of 0.05. Confidence intervals (CIs) will be calculated at the 95% level, reflecting a type I error rate of 0.05.

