## 9.3.4 Skin Prick Test

Results from the Skin Prick Test (SPT) will be listed, including test date, timing of test reading (10, 15 minutes), and measurements (mm) of the following hive/wheals: peanut wheal, peanut erythema/flare, saline wheal, saline-glycerin

erythema/flare, histamine wheal, and histamine erythema/ flare. The summary will incorporate 95% confidence intervals and will include observed values at both 10 and 15 minute time intervals, as well as the maximum observed value for either time interval, with change from baseline and difference in change from baseline between treatment groups where applicable, by treatment group, visit, and hive/wheal type for the ITT population.

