#### **10.12** Physician Global Assessment

A 100-mm VAS will be used by the investigators to assess overall disease activity as a marker for safety (0 = no disease activity, 100 = very severe disease activity). VAS scores will be listed by subject and date. Observed values and changes from baseline will be summarized by treatment group and visit for the Safety population. Summary statistics will include 95% confidence intervals for point estimates of the mean. The treatment difference in mean changes from baseline with 95% confidence intervals will also be summarized.

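### Between-arm differences in peanut IgE, IgG4, skin prick wheal and physician VAS ignore the collected baseline as a covariate; ANCOVA, already used for change in MTD, would usually tighten their intervals at little cost

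*SAP*

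**What the plan says.** Protocol 3.7 and SAP 2.3.2 name changes in peanut IgE, peanut-specific IgG4 and skin prick wheal, and the physician global VAS, as secondary endpoints. The SAP places the VAS among the safety endpoints.

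- **SAP 9.3.3 (IgE, IgG4).** Results are summarised by geometric means with 95% confidence intervals. Exit-to-baseline ratios follow, and the "ratio of those ratios of treatment groups, where applicable, will be presented similarly". On the log scale this is the unadjusted difference between arms in mean change.
- **SAP 9.3.4 (skin prick test).** The summary carries 95% intervals for the 10-minute, 15-minute and maximum readings, "with change from baseline and difference in change from baseline between treatment groups where applicable".
- **SAP 10.12 (VAS).** "The treatment difference in mean changes from baseline with 95% confidence intervals will also be summarized".

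None of the three sections names a model or a covariate. Protocol 9.1.2 only refers back to Section 3.7, and the SAP addendum does not change these analyses. The baselines are available: IgE, IgG4 and the skin prick test at screening (Protocol 6.2), and the VAS at the baseline visit (Protocol 6.3).

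The treatment of MTD is different. SAP 9.3.2 fits ANCOVA to change in log10 MTD with treatment and baseline, and back-transforms to geometric mean ratios. SAP 9.3.1 also adjusts exit MTD for baseline MTD. The baseline-factor models in SAP 9.5 have only response and exit MTD as outcomes.

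**The concern.** The plan adjusts for baseline for one group of endpoints and not for another, gives no reason, and already holds the baseline data for both. No tests are planned for IgE, IgG4, skin prick test or VAS, so the estimated difference and its interval are all the between-arm inference these endpoints will carry. They serve two stated secondary objectives: the immunological effects of treatment, and safety judged by the physician global assessment.

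Two things are at stake with about 25 per arm. One is precision that could be had from data already collected. The other is chance baseline imbalance, part of which a change score carries into the estimate unless the exit-on-baseline slope is 1. SAP 7.8 describes permuted-block randomisation and mentions no stratification on these baselines.

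**Working it through.** **1. The plan's own figure.** The documents state no precision or power for these four measures. The only such figure concerns the primary endpoint. SAP 4 says "This study will enroll approximately 50 subjects randomly assigned in a 1:1 ratio of active to placebo", so about 25 per arm; SAP 6.5 says "all statistical tests will be two-sided, with a significance level of 0.05". SAP 4 claims that "there is at least 80% power to detect an effective CPNA response rate of 58.7 % or more" in one scenario, and "there is at least 80% power to detect an effective CPNA response rate of 56.6% or more" in the other.

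- Dilution by subjects without an exit challenge: 0.25 × 22/25 = 0.22 and 0.667 × 22/25 = 0.587; 0.25 × 20/25 = 0.20 and 0.7075 × 20/25 = 0.566.
- Exact enumeration of the uncorrected Pearson chi-square test with 25 per arm gives power of 80.02% (22% v 58.7%) and 80.21% (20% v 56.6%).

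The stated figure reproduces. It has no bearing on the present point.

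**2. Formula.** Let rho be the baseline-to-exit correlation and k = SD exit / SD baseline. In units of the baseline variance, and for the same sample size:

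- variance of the change score: k² + 1 − 2·rho·k
- residual variance after ANCOVA: k²(1 − rho²)
- difference: (1 − rho·k)²

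The difference is never negative, and is zero only when the exit-on-baseline slope, rho·k, equals 1. The large-sample ratio of interval widths, ANCOVA to change score, is √[k²(1 − rho²)/(k² + 1 − 2·rho·k)]. For k = 1 only, this reduces to √[(1 + rho)/2].

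**3. Numbers.** Neither rho nor k is in the documents, so both are assumed. The table gives the mean ANCOVA width divided by the mean change-score width, from simulation with 25 per arm (10,000 trials per setting, normal data, common slope and SD in both arms, t-based intervals). The large-sample value is in brackets.

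| rho | k = 0.8 | k = 1 | k = 1.25 |
|---|---|---|---|
| 0.3 | 0.717 (0.709) | 0.815 (0.806) | 0.895 (0.886) |
| 0.5 | 0.764 (0.756) | 0.876 (0.866) | 0.956 (0.945) |
| 0.7 | 0.801 (0.792) | 0.932 (0.922) | 1.002 (0.990) |
| 0.8 | 0.809 (0.800) | 0.959 (0.949) | 1.011 (1.000) |
| 0.9 | 0.788 (0.780) | 0.985 (0.975) | 0.986 (0.975) |
| 0.95 | 0.729 (0.721) | 0.998 (0.987) | 0.912 (0.901) |

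With 20 per arm the ratios are almost the same (0.879 at rho 0.5, k = 1). The largest loss in the grid is 1.1% at 25 per arm and 1.5% at 20 per arm, both at rho 0.8 and k = 1.25, where the slope is exactly 1. With k = 1.5 and rho 0.5 the large-sample ratio is √(1.6875/1.75) = 0.982, a narrowing of about 2%.

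**4. Chance imbalance.** The difference in baseline means has standard error √(2/25) = 0.28 baseline SD. A change score carries (slope − 1) times the imbalance into the estimate. At an assumed slope of 0.5, an imbalance of one standard error moves the result by 0.5 × 0.28 = 0.14 SD. An imbalance of 1.96 × 0.283 = 0.55 SD, about a 1-in-20 event, moves it by 0.28 SD. ANCOVA corrects for this using the estimated slope.

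**The case against.** The strongest reply is that nothing here is wrong. An unadjusted difference in change is unbiased under randomisation, and its interval already allows for chance imbalance. That stands. A reader might infer that the planned estimates are biased by regression to the mean, or that the intervals are invalid. The documents do not support either reading: regression to the mean enters the comparison only through chance imbalance, and coverage is sound.

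A second reply is that no decision depends on these measures. SAP 9.3 limits the tested key secondary endpoints to exit MTD and change in MTD, both baseline-adjusted. The measures at issue lie outside the hierarchy, have no planned p-values, and appear in tables titled as summaries (14.2.22, 14.2.23, 14.3.7). Modelling the tested endpoints and describing the rest is a coherent choice, and SAP 8.6 would show any baseline imbalance by arm. This stands as a limit on importance. Showing an imbalance, however, does not correct the estimate for it.

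Third, the size is unknown. The familiar factor (1 + rho)/2 needs equal SDs. That need not hold for IgG4, since Protocol 8.1 expects immunotherapy to induce specific humoral responses. This also stands.

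Fourth, the case is weakest for the VAS, a safety marker that Protocol 6.7 says is not validated for food allergy. The IgE/IgG4 ratio is not a named secondary endpoint. Values beyond the assay limits are set to the limit (SAP 9.3.3), which affects both covariate and outcome. These points shape the fix but do not remove the reason for it.

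**Conclusion.** The point holds as a low-cost gain in expected precision, with correction for chance baseline imbalance, for descriptive secondary endpoints. In large samples the planned intervals are at least as wide as ANCOVA intervals, and equal only at a slope of 1.

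The size rests on assumed rho and k. With equal SDs and 25 per arm, the narrowing runs from about 18% (rho 0.3) to almost nothing (rho 0.95). A smaller exit SD gives more. A larger exit SD with a slope near 1 gives nothing, or a loss of about 1%.

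A reader might go further and conclude that these intervals are definitely wider than the data allow, or that a fixed share of precision is being lost. The documents support neither, because they give no correlation or SD and the gain can vanish. Nor does the point touch the primary result, its power or type I error.

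**What to change.** In SAP 9.3.3, 9.3.4 and 10.12, estimate the treatment difference and its 95% interval by ANCOVA with terms for treatment and the baseline value:

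- **Peanut IgE and peanut-specific IgG4:** log10 scale, back-transformed to a geometric mean ratio. The IgE/IgG4 ratio can be handled the same way as a supporting analysis.
- **Skin prick test:** peanut wheal in mm, using the maximum of the 10- and 15-minute readings, which 9.3.4 already tabulates. Naming one reading avoids choosing among three after the fact.
- **Physician VAS:** in mm, in the Safety population as planned.

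Carry over the unequal-slopes and residual checks of SAP 9.3.2, including its rank-based robustness check. Report by arm and visit how many IgE and IgG4 values sit at the LLOQ or ULOQ. Keep all the unadjusted descriptive summaries. Settle the text before database lock so that the model is not chosen after seeing the results.

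The cost is a few lines of SAP text and some programming, with no new data, visits or subjects. The downside is a little more analysis work and, if the slope is near 1, intervals about 1% wider.

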## 9.3.4 Skin Prick Test

Results from the Skin Prick Test (SPT) will be listed, including test date, timing of test reading (10, 15 minutes), and measurements (mm) of the following hive/wheals: peanut wheal, peanut erythema/flare, saline wheal, saline-glycerin

erythema/flare, histamine wheal, and histamine erythema/ flare. The summary will incorporate 95% confidence intervals and will include observed values at both 10 and 15 minute time intervals, as well as the maximum observed value for either time interval, with change from baseline and difference in change from baseline between treatment groups where applicable, by treatment group, visit, and hive/wheal type for the ITT population.

## 9.4 Immune Tolerance Network (ITN) Samples

Optional blood samples are collected for exploratory analysis by the Immune Tolerance Network. These analyses are will be conducted separately and are outside the scope of this analysis plan. Sample collection dates and times are listed by subject and time point.

## 9.5 Exploratory Efficacy Analysis

The influence of site and other potentially prognostic baseline factors on treatment group differences in the desensitization response rate and MTD at Exit DBPCFC will be explored using the ITT population.

The factors to be explored will be:

- MTD of peanut protein at Screening DBPCFC, in log10 scale
- Age
- Presence of asthma, as recorded as part of allergy history
- Presence of allergic rhinitis or hay fever, as recorded as part of allergy history
- History of allergy to a food other than peanut, as recorded as part of the diet and non-peanut allergy history
- Severity of the peanut allergy, defined as the number of anaphylactic reactions to peanut experienced, divided by the duration of the peanut allergy, and categorized into: subjects with 0 anaphylactic reactions, those with at least one reaction but less than 1 every 5 years, and those with more than 1 reaction every 5 years
- Duration of peanut allergy in months, as recorded as part of allergy history
- Study site
- Peanut IgE level at baseline, in log10 scale
- Maximum SPT peanut wheal diameter at baseline
- VAS score at baseline
- BMI at baseline

If necessary, categorical variables will be pooled such that each pooled level will have at least 3 observations for each treatment group.

For nominal categorical variables, pooling will start with the smallest level which will be pooled with the next larger level until each pooled level has 3 observations for each treatment group. For ordinal categorical variables, pooling will proceed in the same manner but will start with the minimum ordinal value and pool in ascending order. Ties will be broken by sorting (in ascending order) the desensitization rate for CPNA, then by the desensitization rate for placebo, then by the geometric mean of the MTD for CPNA, and then by the geometric mean of the MTD for placebo. If the tie is still not broken, then tied levels (that are subject to pooling) are pooled together as the initial step.

If model parameters for a categorical variable are not estimable, then the minimum number of observations of 3 observations per pooled level for each treatment group will be increased by 1 in the above pooling algorithm until the model parameters are estimable. If the model parameters for a binary categorical variable are not estimable, then that factor will not be explored for its effect.

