4.1 Inclusion Criteria

Subjects who meet all of the following criteria are eligible for enrollment as study subjects:

- 1. Age 4 through 26 years
- 2. Clinical history of allergy to peanuts or peanut-containing foods
- 3. Serum IgE to peanut of $\geq 0.35 \text{ kU}_A/\text{L}$ [determined by the UniCAPTM automated immunoassay system within the past 12 months] and/or a SPT to peanut > 3mm compared to control
- 4. Experience dose-limiting symptoms at or before the 100 mg (143 mg cumulative) dose of peanut protein (measured as 200 mg of peanut flour) or on screening DBPCFC conducted in accordance with PRACTALL guidelines
- 5. Written informed consent from parent/guardian for minor subjects
- 6. Written assent from minor subjects as appropriate (e.g., above the age of 7 years)
- 7. Use of birth control by female subjects of child-bearing potential
- 8. Should not be residing in the same address as another subject in this study
- 9. Cannot have participated in a clinical trial 30 days prior to randomization

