## 8.6 Demographic and Other Baseline Characteristics

Demographic information, in addition to the MTDs of peanut and placebo at the Screening DBPCFC, and the presence of dose limiting symptoms and associated dose levels at the Screening DBPCFC, will be listed for all enrolled subjects. The baseline physicians' global assessment of disease activity will also be listed.

Age in years, at Screening, will be calculated using the following SAS formula: AGE=floor(yrdif( birthdate , Informed Consent date , 'AGE'));

Demographic characteristics, including sex, race, ethnicity, age, height, weight and BMI, will be summarized by treatment group and overall. Baseline immunological characteristics (including total IgE, peanut IgE, peanut-specific IgG4, peanut-specific IgE/IgG4 ratio, and results from SPT) as well as maximum tolerated dose of peanut protein at Screening DBPCFC, and baseline global assessment of disease activity per the VAS, will also be summarized by treatment group and overall.

Demographic and baseline characteristics will be summarized by baseline peanut specific IgE level (less than or equal to 15 kU/L versus greater than or equal to 15 kU/L). Similarly, demographic and baseline characteristics will be summarized by baseline SPT peanut wheal size (less than 8 mm versus greater than or equal to 8 mm).

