#### 9.5.1 Effect on Desensitization Response Rate

The influence of these factors on treatment group differences in the desensitization response rate will be explored using logistic regression. These analyses will be performed on the ITT population.

The logistic regression model will include terms for treatment group and the baseline factor to be explored (e.g. site), and an interaction term between the baseline factor with treatment group. The odds ratio for the treatment group effect will be calculated at each level for categorical variables. The odds ratio for the treatment group effect will be calculated at 3 values for continuous variables (the 25% percentile, median, and 75% percentile). Main effects for treatment group and the baseline factor will also be calculated after dropping the interaction term from the model. A 95% confidence interval and p-value will be presented for each odds ratio using the Wald statistic. The p-value for the interaction term will also be presented and based on the Wald statistic.

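### Two SAP grouping rules mishandle their boundary: exactly 1 anaphylactic reaction per 5 years has no severity class, and a peanut IgE of exactly 15 kU/L falls in both groups

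*SAP*

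**What the plan says.** SAP 9.5 lists 12 baseline factors to be explored in the ITT population for their influence on the treatment difference. One is severity of peanut allergy, "defined as the number of anaphylactic reactions to peanut experienced, divided by the duration of the peanut allergy". The resulting rate is cut into three classes. The lowest holds subjects who never had such a reaction; the wording for the upper two is "those with at least one reaction but less than 1 every 5 years, and those with more than 1 reaction every 5 years". Another factor in the list is how long the allergy has lasted: "Duration of peanut allergy in months, as recorded as part of allergy history". SAP 8.7 also gives it in months.

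Severity enters a logistic regression for response (SAP 9.5.1: "The logistic regression model will include terms for treatment group and the baseline factor to be explored", plus their interaction) and a discrete hazards model for the maximum tolerated dose (SAP 9.5.2).

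SAP 8.6 summarizes demographic and baseline characteristics by peanut-specific IgE, "less than or equal to 15 kU/L versus greater than or equal to 15 kU/L", and by skin prick test wheal, "less than 8 mm versus greater than or equal to 8 mm".

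**The concern.** A grouping rule should place every subject in exactly one group. The severity rule leaves a hole at its upper cut, and the IgE rule overlaps at its only cut.

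For severity, a subject at the cut has no defined level. If the rule is programmed as written, the factor is missing for that subject, and a regression procedure would normally omit the record. The analysis would then cover fewer than the ITT subjects because of a class definition, not because data are missing. There could also be a knock-on effect. SAP 9.5 pools levels with fewer than 3 observations in either treatment group, so one unclassified subject could take a level from 3 to 2 in an arm and change which levels are reported.

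For IgE, a value recorded as exactly 15 kU/L would be counted twice, and the subgroup counts would not add up to the total.

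**Working it through.** **Which values fall in the hole or the overlap.** Write k for the number of reactions and m for duration in months. The rate is 12k/m per year and the cut is 1/5 per year.

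- Class 1: k = 0.
- Class 2: k ≥ 1 and 12k/m < 1/5, that is m > 60k.
- Class 3: 12k/m > 1/5, that is m < 60k.
- Unclassified: k ≥ 1 and m = 60k.

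Checking k from 0 to 7 against m from 1 to 323 leaves exactly five pairs without a class: 1 reaction in 60 months, 2 in 120, 3 in 180, 4 in 240 and 5 in 300. Every other pair has one class. All five are possible under the eligibility range ("Age 4 through 26 years", Protocol 4.1), although 300 months needs a subject aged at least 25.

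For IgE, 14.9 satisfies one condition, 15 satisfies two and 15.1 satisfies one. For the wheal split, 7.5, 8 and 8.5 mm each satisfy exactly one, so that rule is sound.

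**Does anything else in the plan settle the boundary?** No.

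- The pooling rule in SAP 9.5 merges existing levels; it does not assign a subject who has none.
- The blinded review items in SAP 12 do not include severity class.
- The SAP addendum of 10 February 2015 changes neither rule.

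**How often the severity hole would be hit.** The documents give no distribution for age at diagnosis or number of reactions, so these are assumptions: age at diagnosis uniform on 0.75 to 3 years, and 0, 1, 2, 3 or 4 reactions with probabilities 0.30, 0.35, 0.20, 0.10 and 0.05. Age is uniform, either on 4 to 16 (a mostly pediatric sample) or on the full 4 to 26. Duration is age minus age at diagnosis.

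The probability per subject is the sum over k of P(k reactions) × P(duration = 60k months).

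- *Ages 4–26, months.* The age range spans 22 × 12 = 264 months, and each of the durations 60, 120, 180 and 240 has probability 1/264. So p = (0.35 + 0.20 + 0.10 + 0.05)/264 = 0.00265. Expected in 50: 0.13. Chance of at least one: 1 − (1 − 0.00265)^50 = 12%.
- *Ages 4–16, months.* The range spans 144 months. Durations of 60 and 120 are fully reachable; 180 is reachable only with diagnosis by age 1, a fraction 0.25/2.25 = 0.11. So p = (0.35 + 0.20 + 0.10 × 0.11)/144 = 0.0039. Expected in 50: 0.19. Chance of at least one: 18%.

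If every duration were instead recorded as a whole number of years, the per-subject probabilities would be about 12 times larger: 0.70/22 = 0.032 for ages 4–26 (1.6 subjects, 80% chance of at least one) and about 0.047 for ages 4–16 (2.3 subjects, 91%).

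No comparable figure can be given for IgE, because the documents do not give the distribution of values or their recorded precision.

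**The case against.** The strongest reply is that this is proofreading. The SAP does not say that an unclassified subject is to be left out. It specifies the ITT population, and a programmer coding three ordered levels would probably put the tie on one side. Severity is one of 12 factors examined in an exploratory analysis, without multiplicity control (SAP 6.4). Under the SAP's own unit of months, the most likely number of subjects affected is zero.

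Most of that stands. A reader might infer four stronger things that the documents do not support:

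- *That the SAP drops these subjects.* It does not say so; exclusion follows only from literal coding and usual handling of a missing factor level.
- *That about two subjects are almost certain to be lost.* That needs whole-year durations throughout. The SAP specifies months, and nothing in the documents shows that values cluster at whole years, although recalled durations might.
- *That the baseline groupings in general are faulty.* The wheal split, in the same section as the IgE split, is a correct partition.
- *That the IgE overlap affects an efficacy analysis.* IgE enters the models on a continuous log10 scale, so the 15 kU/L cut is used only for description.

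What the reply does not remove is that the boundary is unassigned, so someone must choose a side. As the plan stands, that choice could be made in programming, after treatment assignments are known.

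**Conclusion.** The point holds as a minor correction. Each of the two rules fails at one value, and nothing else in the SAP or its addendum repairs it. The expected effect is about 0.1 to 0.2 of 50 subjects in the severity gap, with a 12% to 18% chance of at least one. Both figures rest on the assumed age, diagnosis and reaction distributions and on durations precise to the month. One subject is 1/25 = 4% of an arm, but only in exploratory interaction models. The IgE overlap can disturb only the counts in Tables 14.1.4 and 14.1.7, and only if a value is recorded as exactly 15. The primary analysis and the two key secondary analyses use neither grouping and are unaffected.

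**What to change.** Before unblinding, close one boundary in each rule. For example, define the top severity class in SAP 9.5 as a rate of 1 or more reactions every 5 years, and define the IgE groups in SAP 8.6 as below 15 kU/L versus 15 kU/L or above, in the same form as the wheal split. Which side takes the boundary is the sponsor's choice; what matters is that it is written once and in advance. The cost is a few words in the SAP or its addendum, with no change to data collection, sample size or any confirmatory analysis.

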6.1 Enrollment and Randomization

Subjects will have an initial screening DBPCFC consisting of both a peanut challenge and a placebo challenge before randomization. The peanut and placebo challenges will be conducted in a double-blind fashion, using study products provided by the unblinded site pharmacist or nutritionist. Those reacting to ≤ 100 mg of peanut protein (143 mg cumulative) will be randomized in a 1:1 ratio to peanut OIT or placebo. Those able to successfully consume >100 mg of peanut protein during their DBPCFC will not be eligible for the study. Randomization will be done via TEMPOTM. If accrual capacity is adequate, each of the expected 8 sites should enroll approximately 6-8 subjects each. Because of the requirement for the peanut DBPCFC, the screening and baseline visits may be conducted in more than 1 day.

The study procedures are tabulated in **Appendix 1** and are listed per visit below.

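### SAP 9.5 orders sites of equal size by their observed response rates before pooling them, which inflates the exploratory treatment-by-site interaction test when site sizes are similar

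*SAP*

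**What the plan says.** SAP 9.5 lists study site among the baseline factors whose influence on the treatment difference will be explored. Categorical factors are pooled until each level has at least 3 observations in each arm. For a nominal factor such as site, the smallest level is merged with the next larger one, and so on. For an ordinal factor, merging starts at the lowest value. When levels tie, the SAP says: "Ties will be broken by sorting (in ascending order) the desensitization rate for CPNA, then by the desensitization rate for placebo". The next keys are the geometric mean MTD for CPNA and then for placebo. If the model still cannot be estimated, the minimum of 3 is raised by 1 and the pooling repeated.

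SAP 9.5.1 then fits a logistic regression of desensitization response with a treatment-by-factor interaction. SAP 9.5.2 does the same for exit MTD with the discrete hazards model. Each reports a Wald p-value for the interaction.

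Protocol 6.1 expects, if accrual capacity is adequate, that "each of the expected 8 sites should enroll approximately 6-8 subjects each". SAP 7.8 describes a central permuted-block schedule and states no stratification by site. Pooling is not among the items that SAP Section 12 fixes at the blinded review, and the addendum leaves 9.5 unchanged.

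**The concern.** The tie-break keys are the same outcomes, split by the same arms, that the interaction models analyze. Ordering tied sites by ascending CPNA response places low-responding sites next to each other and high-responding sites next to each other, so neighbors merged into one pool tend to resemble one another. Chance variation between sites that pooling would otherwise average out is kept as a difference between pools. The interaction test then sees more heterogeneity than the data hold, and a reader of the table of odds ratios by pooled site could not tell why.

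What is at stake is a false impression that the effect of CPNA varies by site.

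**Working it through.** **1. Inputs and the plan's own figure.** SAP 4 states: "This study will enroll approximately 50 subjects randomly assigned in a 1:1 ratio of active to placebo", so 25 per arm. In its first scenario "the effective placebo response rate in the ITT analysis is assumed to be 22% or less" and "there is at least 80% power to detect an effective CPNA response rate of 58.7 % or more". In its second, "the effective placebo response rate in the ITT analysis is assumed to be 20% or less" and "there is at least 80% power to detect an effective CPNA response rate of 56.6% or more". The effective rates follow from those among subjects who are challenged: 0.88 × 25% = 22% and 0.88 × 66.7% = 58.7%; 0.80 × 25% = 20% and 0.80 × 70.75% = 56.6%. Enumerating both binomials for the uncorrected two-sided Pearson chi-square test with 25 per arm gives power of 80.0% and 80.2%, so the stated power reproduces. The documents give no figure for the pooling rule or the interaction test. SAP 6.5 supplies the level: unless stated otherwise, "all statistical tests will be two-sided, with a significance level of 0.05".

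**2. Would the tie-break be used?** Take six sites of 6 and two of 7 (6 × 6 + 2 × 7 = 50). As a rough check, treat assignments within a site as fair independent draws.
- A site of 6 has 3 in each arm with probability 20/64 = 0.3125, so it falls short with probability 0.6875.
- A site of 7 splits 3-4 or 4-3 with probability 70/128 = 0.547, so it falls short with probability 0.453.
- Expected sites short of 3 per arm: 6 × 0.6875 + 2 × 0.453 = 5.0 of 8.
- Probability that none is short: 0.3125^6 × 0.547^2 ≈ 0.0003.

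Simulation with permuted blocks of 4 agrees. At least one site is short in 99-100% of trials with sites of 6-8. A short site ties in size with another site in 98-100% of those trials, and in 84% when sites are very uneven.

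**3. Which factors can tie?** Asthma, allergic rhinitis and other food allergy are binary, so pooling leaves nothing to order. Allergy severity has three distinct ordered levels. The remaining factors apart from site are continuous. In practice the rule acts on study site alone.

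**4. Effect on the 9.5.1 test.** Trials were simulated with the same response rates at every site. Sites were pooled by the SAP rule, including the estimability step, with ties broken either by observed CPNA then placebo response, or at random as a stand-in for any outcome-blind key. In pooled level k with 2 × 2 cells a, b, c, d:

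θ_k = log(ad/bc), v_k = 1/a + 1/b + 1/c + 1/d

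W = Σ(θ_k − θ̄)²/v_k, where θ̄ is the inverse-variance weighted mean, referred to chi-square on K − 1 df.

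This is the Wald interaction test of the logistic model with treatment, pooled site and their product. It cannot be computed if any cell is zero, which is what triggers the estimability step.

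Rejection at 0.05 at 22% v 58.7%, among trials where the test could be run, over three separately programmed simulations (one with two readings of the pooling steps):

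| Site sizes | SAP tie-break | Random tie-break |
|---|---|---|
| Six of 6, two of 7 | 6.0-7.2% | 1.5-2.6% |
| Random in 6-8 | 3.0-4.0% | 1.7-2.5% |
| Very uneven | 1.9-2.5% | 1.9-2.6% |

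In the first layout, 20% v 56.6% gave 7.0% v 1.0%, and 40% v 60% gave 7.5% v 1.8%. Monte Carlo error is about 0.3 percentage points.

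The contrast does not come from conditioning on the test being possible. In one run of the first layout the test could be run in 88.9% (SAP) and 97.2% (random) of trials, so over all trials the rates are 0.889 × 6.5% = 5.8% and 0.972 × 1.6% = 1.6%.

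The mechanism shows directly in the variance of the CPNA rate across pooled levels in that layout, before the estimability step. It rises from 0.054-0.055 to 0.069-0.071.

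**5. The estimability step.** With the SAP rule the threshold had to be raised in 80-94% of trials. Another run gave 83-92% under either tie-break.

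**The case against.** The case for leaving the rule alone has several parts.

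- **Outcome is only a secondary key.** Size or ordinal value sorts first. This stands, and it limits the point to study site. A reader of the tie-break sentence might infer that the pools for every categorical factor are built from the outcome. The list of factors does not support that.
- **The size of the effect rests on assumed site sizes.** This also stands. The protocol's site numbers are expectations that depend on accrual. The test exceeds 5% only in the near-equal layout, which is the most prone to ties. When sizes vary between 6 and 8 it remains conservative, and when sites are very uneven the two rules cannot be told apart. A general claim that the interaction test is anti-conservative would be wrong.
- **Nothing depends on the result.** SAP 9.5 is labelled exploratory, no action is tied to the interaction p-value, and the primary and key secondary analyses use no pooled sites. This stands in full.
- **The rule is algorithmic and prespecified.** True, so there is no analyst discretion to worry about. Prespecification does not remove the distortion, though, because the algorithm itself takes the outcome as input.
- **Changing the tie-break does not make the pools outcome-blind.** Correct. Raising the threshold is triggered by arms with 0% or 100% response within a level. That limits what the change achieves but gives no reason to keep the tie-break, for which the SAP offers no rationale.

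**Conclusion.** The point holds for study site in the exploratory analyses. The tie-break would almost certainly be used, and under no true site effect it raises rejection of the 9.5.1 treatment-by-site test at 0.05 from about 2% to 6-7% with near-equal sites and from about 2% to 3-4% with sizes varying in 6-8. With very uneven sites there is little or no effect.

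These figures assume equal response rates at all sites, the SAP's planning rates, no site stratification, blocks of 4 where the block size had to be assumed, and site size counted as total subjects. The MTD keys were not simulated.

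Two further inferences are not supported. The 9.5.2 hazard model uses the same pools and a related outcome, so a similar distortion is plausible, but no size can be given for it. The conclusions on the primary and key secondary endpoints are not touched. This is a minor point, worth acting on because the correction is free.

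**What to change.** In SAP 9.5, delete the response-rate and MTD tie-breaks and order tied sites by a fixed outcome-blind key, such as ascending site number. No replacement is needed in practice for the other categorical factors. The fallback that merges levels still tied after all keys then becomes redundant for site.

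The cost is one sentence in the SAP and slightly simpler code, with no change to data, sample size or confirmatory analyses. The ordering key can be written down before unblinding, although the pools themselves must still wait for treatment assignments because the minimum is set per arm.

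Because the estimability step still depends on outcome, add a line stating that pooled-site interaction results in 9.5.1 and 9.5.2 are descriptive.
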